11.1 Presentation of results

Assumed continuously distributed variables expresses by mean values with 95% confidence intervals ³⁷. As an index of dispersion Standard Deviation (SD) will be used. Categorized variables will be expressed in Contingency Tables ³⁸.

11.2 Statistical methods

The differences between the groups will be considered significant if the p-value is less or equal to 5 %. Comparison between groups regarding assumed continuously distributed variables will be performed by using analyses of covariance (ANCOVA) with a basic observation as covariance and repeated measurements ³⁹. Contingency table analyses will be used for comparison of discrete distributed variables.³⁸. Correlation and regression analysis will be performed to estimate the connection in the development between variables.

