5.7.3 Bone Turnover markers

Collagen 1 (CTX-1) Procollagen 1 (PINP) Parathyroid hormone (PTH) Bone specific alkaline phosphatase (BALP)

5.7.4 Sex hormones:

Estradiol Progesterone Testosterone LH FSH

5.7.5: Haematology

Haemoglobin (Hgb) HbA₁C

5.8: Diet registration

Diet registration will be performed by the participants. The daily intake of all food will be recorded daily for four days consecutively at screening and every eight weeks during the study. A pre-evaluated questionnaire based "diet.no" will be used and recorded on an electronical diet APP by the participants. The diet registration will be supervised by a qualified monitor. The results will be evaluated by the investigating team.

5.9: Menstruation status

To control the hormone blood sample results to female XCS, this group will be interviewed about their menstruation status. This includes menarche length, cycles day and use of hormonal contraceptives.

5.10: Cheese, supplement, and activity registration

The cheese, supplement of vitamin D and activity will med recorded in a form for daily registration. The activity will be recorded weekly. The parameters to be recorded are low- and high intensity running and roller-ski in hours, and low- and high-load strength exercise. The forms are handed out every fourth week of the study and collected by the investigator or the research assistant.

5.11: Compliance

The participants must eat their daily prescribed dose of cheese and vitamin D, register their activity weekly, and fill in their diet APP 4 days before their control every 8 weeks.

5.12: Adverse Events (AE)

5.12.1: Common Terminology Criteria for Adverse Events version 4.0 (CTCAE)

The CTCAE is divided in 26 System Organ Class (SOC) in accordance with the MedDRA hierarch. Within each SOC, AE are listed and accompanied by descriptions of severity or grade:

- Blood and lymphatic system disorders (11 Items)
- Cardiac disorders (36 Items)
- Congenital, familial, and genetic disorders (1 Items)
- Ear and labyrinth disorders (9 Items)
- Endocrine disorders (11 Items)
- Eye disorders (25 Items)
- Gastrointestinal disorders (117 Items)
- General disorders and administration site conditions (24 Items)
- Hepatobiliary disorder (16 Items)
- Immune system disorders (6 Items)
- Infections and infestations (76 Items)
- Injury, poisoning and procedural complications (78 Items)
- Investigations (38 Items)
- Metabolism and nutrition disorders (24 Items)

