The patient factors to be recorded in the study will be age in years from birth to the screening visit, height in cm and body weight in kg. Previous medical history, duration of any disease in months from the final diagnosis to the screening visit, previous and on-going treatment of the disease will be observed. During each physical examination, body weight, concomitant disease and treatment will be recorded. Additionally, vital signs defined as Systolic and Diastolic blood pressure in mmHg and Heart rate in beats/min will be recorded in sitting position after five-minute rest. To eliminate any vitamin D disturbances the participants are provided supplement of 40μ g Vitamin D from the start till the end of the study.

VI: Study procedure

6.1: Definitions

Important definitions are:

- 1) Osteocalcin Ratio (R₀): cOC (carboxylated Osteocalcin)/ uOC (undercarboxylated osteocalcin).
- 2) Bone Mineral Density (BMD) and Trabecular Bone Score (TBS).
- 3) Lean Body Mass (LM) extracted from the body composition outcomes obtained from DXA.
- 4) RMR ratio (resting metabolic rate ratio). Observed RMR/ 22x FFM+ 500 (The Cunningham formula)
- 5) Peak VO2 which is maximal oxygen uptake.

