11.3 Power analysis and sample size determination

With a significant level of 5%, a power of 90% and a clinically relevant difference in total osteocalcin increase of one-time SD between the two groups, at least 24 XCSs in each group must be included. By correcting for dropouts during the first part of the study, 30 XCS will be included in each group. Totally 60 XCSs will be recruited for participation²⁹.

XII: Operational Matter

12.1: Investigator's agreement

Before the start of the trial the investigator will confirm the agreement to participate in the trial by signing the Investigator's Agreement Form (Appendix IX).

12.2: Instructions

The investigators will give instructions by the data manager group and the clinical monitor supported by the project manager at the start-up visit and during the study.

12.3: Amendments to the protocol

Changes in the protocol can be required by the Ethical Committee, project manager or TINE. Changes must be written in amendments approved by the steering committee, investigator, Tina SA, and Ethical Committee. Amendments must be numbered and be together with the original protocol.

It is forbidden to add new parameters consisting of measurements on the patients in the study unless they are covered as amendments in the protocol or taken due to the health and safety of the patient.

12.4: Protocol deviations

Deviations from the protocol should be restricted as much as possible and will be fully recorded and justified. The Project manager will be informed as soon as possible of all protocol deviations.

12.5: Compliance monitoring

The Project manager and the Investigator will ensure that the site is suitable for the trial and that the participating XCS is well informed of the particulars of the trial. The Project manager and Investigators should check, protocol compliance, handling of the test articles and recording of data during the critical stages of the trial. A report is prepared of each visit and kept in the trial master file (TMF).

12.6: Responsibilities

The investigator will acknowledge the responsibilities and the agreement to participate in the trial by dating and signing the agreement form. The Project manager will verify that adequate arrangements have been made for the observations, measurements and recording of the data.

12.7: Confidentiality

The obtained data and results will be used by TINE for marketing purpose. The main study database will be stored in the product database of TINE.

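### Sections 11.1 and 11.2 give every continuous variable arithmetic means and one baseline-adjusted ANCOVA, with no provision for sex or a log scale; this costs precision for the sex hormones and, to a lesser degree, for R0

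*Protocol*

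**What the plan says.** Protocol section 11.1 sets the presentation: "Assumed continuously distributed variables expresses by mean values with 95% confidence intervals", with SD as the measure of spread. Section 11.2 sets the test: "Comparison between groups regarding assumed continuously distributed variables will be performed by using analyses of covariance (ANCOVA", with the baseline value as covariate and repeated measurements. The decision rule is also common to all variables: "The differences between the groups will be considered significant if the p-value is less or equal to 5" percent. Neither section mentions sex, a transformation or a by-sex analysis.

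The variables at issue are these:
- R0, defined in section 6.1 as "cOC (carboxylated Osteocalcin)/ uOC (undercarboxylated osteocalcin"). Section 5.1 makes it secondary in both study parts.
- The sex hormones listed in section 5.7.4: "Estradiol Progesterone Testosterone LH FSH". Section 1.7 calls them supporting variables.

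Sections 1.5 and 4.1 stratify randomisation by sex, because the cheese dose differs and because an earlier dose-response study found that men and women responded differently. Section 5.9 adds a menstruation interview so that women's hormone results can be interpreted. The sample size in section 11.3 is given per cheese group over both sexes; the flow diagram in section 6.8 shows 15 per sex and cheese.

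**The concern.** The design treats sex as important enough to stratify on, but the stated model names only the baseline value. Leaving out a stratification factor that predicts the outcome leaves its variation in the residual.

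Scale adds to this for two kinds of variable. If hormone levels differ widely between men and women, a raw-scale model takes most of its residual variance from the sex with the larger values and fits one baseline slope to both. The estimated difference in units then sits between two quite different sex-specific differences. R0 is a quotient, so it may be right-skewed, and an arithmetic mean is then an inefficient summary.

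At stake are the precision of the R0 and hormone results and the meaning of the hormone estimate.

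**Working it through.** **1. The plan's own sample size.** Section 11.3 gives: "With a significant level of 5%, a power of 90" percent; a "clinically relevant difference in total osteocalcin increase of one-time SD between the two groups"; and "at least 24 XCSs in each group must be included". Sidedness is not stated.

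- Normal approximation, two-sided: n = 2(z₀.₉₇₅ + z₀.₉₀)² / (Δ/SD)² = 2(1.960 + 1.282)² / 1² ≈ 21.0, so 22 per group.
- Exact t: power is 0.8997 at 22 and 0.912 at 23, so 23 per group. At the stated 24 it is 0.924.
- One-sided testing would need 18, so two-sided is the match.
- Dropout: 24 / (1 − 0.20) = 30. The 20% is implied (6/30), not stated.

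The tOC figure reproduces to within two skiers.

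**2. What a combined raw mean would describe.** Assume that one sex has 10 times the level of the other, with the same log-SD and the same percent effect.

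- The difference in units is then 10 times as large in the higher sex. With equal strata the combined difference is (10 + 1)/2 = 5.5 times that of the lower sex and 5.5/10 = 0.55 of that of the higher sex.
- The variance ratio is 10² = 100, so the higher sex supplies 100/101 = 99% of the within-sex variance.

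**3. Power by simulation.** Assumptions: lognormal data, 24 per group (12 per sex and group), one follow-up, log-scale correlation with baseline ρ = 0.6, and 4000 runs per cell.

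- Log baseline: μ(sex) + σe₀.
- Log follow-up: μ(sex) + σ[ρe₀ + √(1 − ρ²)e₁] + δ × group.
- Effect: δ = 0.96 × σ × √(1 − 0.36) = 0.768σ. This is a ratio of e^0.154 = 1.17 at σ = 0.2 and e^0.614 = 1.85 at σ = 0.8.
- Noncentrality for the log-scale model: 0.96 × √(24/2) = 3.33, which fits the reference power of about 90%.

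σ is the log-SD.

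| Sex gap | Model | σ = 0.2 | 0.3 | 0.5 | 0.8 |
|---|---|---|---|---|---|
| none | raw, no sex | 0.89 | 0.88 | 0.85 | 0.75 |
| none | log + sex | 0.90 | 0.90 | 0.90 | 0.89 |
| 1.5-fold | raw, no sex | 0.85 | 0.85 | 0.82 | 0.74 |
| 1.5-fold | raw + sex | 0.88 | 0.87 | 0.83 | 0.73 |
| 1.5-fold | log + sex | 0.90 | 0.90 | 0.90 | 0.89 |
| 10-fold | raw, no sex | 0.60 | 0.59 | 0.55 | 0.49 |
| 10-fold | raw + sex | 0.67 | 0.65 | 0.61 | 0.54 |
| 10-fold | log, no sex | 0.84 | 0.83 | 0.84 | 0.86 |
| 10-fold | log + sex | 0.89 | 0.88 | 0.90 | 0.90 |

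- Without a sex gap, the raw scale costs about 1 to 5 points up to log-SD 0.5 and about 14 points at 0.8.
- With a 10-fold gap, a sex term on the raw scale wins back only 4 to 7 points. Most of the loss comes from the scale.
- With no true effect, the raw model without sex rejects in 0.033 to 0.053 of trials. Errors are at or below the nominal level, apart from simulation noise.

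The log model simulated here has a sex intercept and a common slope. Sex-specific slopes would add one parameter and were not simulated.

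**The case against.** The strongest reply is that the protocol nowhere says untransformed and nowhere says pooled. ANCOVA on log values would comply with section 11.2. Section 5.1 speaks of sex arms, the flow diagram shows counts by sex, and section 5.9 gives women's hormones separate attention. Scale is commonly left to the SAP, which is not at hand. This stands as far as it goes: silence on transformation alone would be no finding, and both words are inferences from the text. What remains is that the protocol does state a blanket rule, means with SD and one ANCOVA, and in describing that model names the baseline but not its own stratification factor.

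It is also fair that the simulation favours the log scale by construction, since the data are lognormal and the effect is multiplicative. The figures show what is lost if the data look like that; they do not show that they will.

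Several stronger readings are tempting but not supported:
- **A few extreme values decide the result, or false positives rise.** The simulated error rates do not show this; the harm is lost power and a less readable mean.
- **The tOC comparison is compromised.** Nothing in the protocol shows it, and the sample size reproduces.
- **Osteocalcin and all bone markers should be logged too.** No defect is shown for them, and section 11.3 powers tOC as a one-SD difference in increase, so a ratio scale would change that target.
- **Serum MK-9(4H) will be undetectable in the Norvegia group.** Table I reports cheese content, not serum levels, and no serum detection limit is given.
- **The mean of R0 depends on which component is the denominator.** True in general, but sections 2.1 and 6.1 both fix carboxylated osteocalcin as numerator, so no choice is left open.

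**Conclusion.** The point holds in a limited form. Followed as written, sections 11.1 and 11.2 give the sex hormones, and R0 if it is strongly skewed, a less efficient analysis than the same data allow, and give the hormones a combined difference that may describe neither sex.

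For R0 the loss is small, about 1 to 5 points of power, unless its log-SD is well above 0.5. For hormones it can be large, down to 0.49 to 0.67 against about 0.90, but only under an assumed 10-fold sex gap that the documents neither give nor exclude.

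The affected variables are secondary or supporting. The omission of sex from the stated model is the firmest part, because it rests on the protocol's own reason for stratifying and needs no assumption about distributions.

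**What to change.** - **Section 11.2, all continuous variables:** add sex to the ANCOVA model.
- **Section 11.2, sex hormones:** analyse natural logs with a sex-specific intercept and a sex-specific slope on log baseline.
- **Section 11.2, R0:** analyse natural logs with log baseline as covariate.
- **Section 11.1:** report R0 and the hormones as geometric-mean ratios with 95% confidence intervals.
- **tOC and the bone markers:** keep them on the scale used for the power calculation.

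The cost is wording and code; no new data and no change in sample size are needed. The drawback is that hormone and R0 effects are read as percent differences instead of units.

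Analysing hormones separately within each sex is an alternative, but leaves about 15 per cell. By the exact t calculation, power for a one-SD difference is 0.75 at 15 per group against 0.97 at 30. The joint model with sex-specific terms is therefore preferable. The wording should be settled before results are seen, because the trial is open and a scale chosen later could follow the result.

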11.3 Power analysis and sample size determination

With a significant level of 5%, a power of 90% and a clinically relevant difference in total osteocalcin increase of one-time SD between the two groups, at least 24 XCSs in each group must be included. By correcting for dropouts during the first part of the study, 30 XCS will be included in each group. Totally 60 XCSs will be recruited for participation²⁹.

XII: Operational Matter

12.1: Investigator's agreement

Before the start of the trial the investigator will confirm the agreement to participate in the trial by signing the Investigator's Agreement Form (Appendix IX).

12.2: Instructions

The investigators will give instructions by the data manager group and the clinical monitor supported by the project manager at the start-up visit and during the study.

12.3: Amendments to the protocol

Changes in the protocol can be required by the Ethical Committee, project manager or TINE. Changes must be written in amendments approved by the steering committee, investigator, Tina SA, and Ethical Committee. Amendments must be numbered and be together with the original protocol.

It is forbidden to add new parameters consisting of measurements on the patients in the study unless they are covered as amendments in the protocol or taken due to the health and safety of the patient.

12.4: Protocol deviations

Deviations from the protocol should be restricted as much as possible and will be fully recorded and justified. The Project manager will be informed as soon as possible of all protocol deviations.

12.5: Compliance monitoring

The Project manager and the Investigator will ensure that the site is suitable for the trial and that the participating XCS is well informed of the particulars of the trial. The Project manager and Investigators should check, protocol compliance, handling of the test articles and recording of data during the critical stages of the trial. A report is prepared of each visit and kept in the trial master file (TMF).

12.6: Responsibilities

The investigator will acknowledge the responsibilities and the agreement to participate in the trial by dating and signing the agreement form. The Project manager will verify that adequate arrangements have been made for the observations, measurements and recording of the data.

12.7: Confidentiality

The obtained data and results will be used by TINE for marketing purpose. The main study database will be stored in the product database of TINE.

The steering committee has the demand and the right to try the results published in an international medical journal. The draft of the manuscript must be presented for the sponsor for comments, discussion and final approve. The sponsor cannot stop the publication unless it is proved that publication of the results may destroy for marketing of the product.

The results from the study cannot be presented in any meeting or congresses without approval by the sponsor. The data obtained in this study must be handled confidentially by the member of the steering committee until the first registration of the product is performed.

XIII Amendment

13.1: Menstruation status (pkt. 5.9, 1.6 & 1.10)

To control the hormone blood sample results to female XCS, this group will be interviewed about their menstruation status. This includes menarche length, cycles day and use of hormonal contraceptives.

13.2: Inclusion criteria (pkt. 3,1 & 3.2 and 1.4)

3.1: Reference population. Active athletes of both sexes from 16 years of age representing sports with equal loading.

3.2: Study population. Active XCS from 16 years of age.

1.4: Population and sampling. The study population consists of active XCS of both genders past 16 years of age.

13.3: Cheese dose(pkt.1.6, 4.2 & 6.3.1)

4.2: The daily amount of cheese will be equal in the two cheese-groups with 5 slices (75g) for females and 6 slices (90g) for males.

13.4: Study procedure (pkt.1.6 & 5.2, 5.3 & 6.1, 6.2).

6.2: DXA investigation of BMD and TBS will be performed, and RMR measured together with muscle strength, LM and Peak VO₂ before starting the clinical part.

XIV References

- Mountjoy M. Sundgot-[name] JK, Bourke LM, Ackerman KE,Blauwet C, Constantini N, Lebrun C, Lundy B, Melin AK, Meyer NL, Sherman RT, Tenforde AS, Torstveit MK, BudgettR; IOC consensus statement on relative energy deficiency in sport (RED-S): 2018 update. Br J Sports Med.
- 2. Sundgot-[name] J, Thorstveit MK. Prevalence of eating disorders in etlite athletes is higher than in the general population. Clin J Sport Med 2004; 14:25-32.

- 14.5: Patient information
